4.2.1.8 Tipping Point analysis

Tipping point analyses will also be implemented as a supportive analysis for the primary efficacy endpoint only.

The objective of the tipping point analyses is to evaluate the sensitivity of results to departures from the missing at random assumption and to identify the point at which departures cause results "tip" from statistically significant to statistically insignificant. As such, these tipping point analyses will only be performed if the primary efficacy analysis results in a statistically significant treatment effect ($p<0.05$).

In this sensitivity analysis, data for study participants after date of discontinuation of treatment for any reason (as defined in Section 3.4) will be changed to missing prior to imputation but will not be changed to non-response after imputation.

As a first step, the worst-case scenario will be evaluated for the primary endpoint (ASAS40 at Week 16). All missing primary endpoint values for study participants randomized to BKZ (where missing values are due to, e.g., discontinuation of treatment or missing components of the primary endpoint) will be imputed as non-responders, while all missing values for placebo-randomized study participants will be imputed as responders. While there is little justification for such an approach, it makes the most putative assumption possible against a bimekizumab treatment effect. After applying this imputation approach, a logistic regression model consistent with the one described for the primary analysis will be applied. If the p-value for the odds ratio of bimekizumab versus placebo is less than 0.05, then no further tipping point analyses are needed.

If the analysis based on the worst-case scenario results in a p-value greater than 0.05, then additional tipping point analyses will be performed to identify the point at which results switch from significant to insignificant. In this analysis, a shift parameter or delta adjustment is applied

to missing, and subsequently imputed values (where missing values include observations after the date of discontinuation of treatment and any other missing values). These delta adjustments will be implemented on the Week 16 imputed values only for each component of ASAS40, as follows:

1. Data after date of discontinuation of treatment for any reason will be set to missing.
2. The same MCMC method described in Section 4.2.1.4.1 Step 2a and 2b will be implemented for non-monotone (intermittent) missing pattern values, using the same imputation model. This will be based on 100 sets of imputations.
3. Based on the 100 datasets obtained in Step 2b, a monotone regression model will be applied (using the same imputation model as in Step 2a) as described in Section 4.2.1.4.1 Step 2. This will be based on 1 imputation.
4. Delta adjustments will be made to all Week 16 imputed values only, independently in each treatment group as described in detail below.
5. Delta adjusted imputed values will be truncated so that they are within the range of allowable values for each component.
6. Following the delta adjustments for the individual components, the composite binary endpoint (ASAS40) will then be derived based on the multiply delta-adjusted imputed data sets obtained for each component as described in Section 4.2.1.4.1.

Each of the 100 imputed datasets will then be analyzed using a logistic regression model with factors of treatment group, region, and prior TNF α inhibitor exposure as fixed effects.

7. The results obtained from the 100 logistic regression analyses in Step 6 will be combined for overall inference using Rubin's rules, and the results obtained for each shift parameter will be presented in a single table.
8. Step 3 to Step 7 will be repeated so that, at each iteration, missing values are adjusted with a larger delta than at the previous iteration. Depending on the results obtained, shift parameters with more granularity (eg, 1.1, 1.2, 1.3, 1.4, 1.5, 1.6, 1.7, 1.8, 1.9) may also be investigated. The process will go on until the p-value for the odds ratio between bimekizumab and placebo is no longer statistically significant (ie, ≥ 0.05). The odds ratio, 95% CI, and p-values obtained for each value of delta will be combined in one single table.

The delta adjustments performed here assume that study participants randomized to bimekizumab and who have missing data have a lower probability of response compared to study participants randomized to placebo with missing data. Therefore, for endpoints where high scores are associated with a more favorable outcome:

- A negative shift is applied to the imputed value for study participants randomized to bimekizumab in order to decrease the imputed value and reduce the likelihood of response.
- A positive shift is applied to the imputed value for study participants randomized to placebo in order to increase the imputed value and increase the likelihood of response.

For endpoints for which high scores are associated with a less favorable outcome:

- A positive shift is applied to the imputed value for study participants randomized to bimekizumab in order to increase the imputed value and reduce the likelihood of response.

- A negative shift is applied to the imputed value for study participants randomized to placebo in order to decrease the imputed value and increase the likelihood of response.

To start, imputed values within each continuous component, will be adjusted by the same integer value in each treatment arm. Imputed values will initially be adjusted by values of 1, 2, and 3. After these initial analyses, additional adjustment values may be tested to better identify the point at which results "tip". More robust primary analysis results will require larger adjustments to tip the results from significant to insignificant.

4.2.1.9 Treatment Policy Strategy

Another supportive analysis will be performed on the primary efficacy endpoint to address intercurrent events.

The treatment policy strategy will include all available data observed at the week of interest (Week 16) regardless of the occurrence of intercurrent events. This means the analysis includes on- and off-treatment values collected after study participants prematurely discontinued study treatment but agreed to remain on the study and continued to attend visits and provide assessments at those visits. Those observed values will be analyzed according to the study participant's randomized treatment. Study participants for whom efficacy data cannot be obtained at the week of interest, despite attempts to retain them in the study, will have their data imputed using MI under the assumption of MAR (ie, MI-MCMC/Monotone Regression).

In practice, the Step 1 for the non-composite binary endpoints described in Section 4.2.1.4.1 will not apply, and the final ASAS40 response will not be changed to "non-responder" at the end of the imputation step (ie, Step 4) for study participants having an intercurrent event.

4.2.1.10 Observed Cases analysis

The observed case analysis only applies where study participants are still on the original randomized treatment. Therefore, data collected after the date of study treatment discontinuation (for any reason) will not be considered in observed case summaries.

In addition, for all endpoints except the ASAS response for which the response is still calculable when there is only 1 component with missing data (see Section 4.2.1.1), all other missing data will also be excluded.

4.2.1.11 Last Observation Carried Forward

The LOCF analysis will only apply for the continuous secondary efficacy endpoints that are part of the testing hierarchy, if the reference-based multiple imputation analysis does not converge (even after having dropped the covariates).

Post-Baseline missing data will be imputed by carrying forward the last available observation before the missing visit. Baseline data can be carried forward.

If a study participant has a value that is missing at Baseline, then the study participant will not be included in the analysis.

4.2.1.12 Allowed ranges for continuous efficacy variables

The table below indicate the possible range of values for each continuous efficacy variable:

Table 4–2: Allowable ranges for continuous efficacy variables

Variable	Minimum	Maximum
BASDAI	0	10
BASFI	0	10
BASMI	0	10
Lateral spinal flexion	0.75	25
MASES	0	13
PGADA	0	10
Total NSP	0	10
SF-36 MCS ^a	-3.33	80.09
SF-36 PCS	5.02	79.78
SF-36 Bodily Pain	21.68	62
SF-36 General Health	18.95	66.5
SF-36 Mental Health	11.63	63.95
SF-36 Physical Functioning	19.26	57.54
SF-36 Role Emotional	14.39	56.17
SF-36 Role Physical	21.23	57.16
SF-36 Social Functioning	17.23	57.34
SF-36 Vitality	22.89	70.42
ASQoL	0	18

^a SF-36 ranges are used for imputation purposes only. Any observed values outside the ranges based on norm-based scores will be reported as calculated in all tables and listings.

4.2.2 Handling of missing data for AE

For analyses of AEs, a complete date must be established to correctly identify the AE as occurring during treatment or not. For purposes of imputing missing components of partially reported start and stop dates for AEs, the algorithms listed below will be followed. In the event of ambiguity or incomplete data which makes it impossible to determine whether the AE was treatment emergent, the AE will be considered treatment emergent. If an imputed date occurs after a study participant's date of death, the imputed date will be set to the date of death.

Although the algorithms for treatment-emergence depend on the onset date, imputation rules are provided for stop date as well, as these may be needed for certain statistical analyses, such as an analyses of AE prevalence or AE duration.

Start and stop dates of AEs will be displayed as reported in the study participant data listings (ie, no imputed values will be displayed in data listings).

Imputation of Partial Start Dates

- If only the month and year are specified and the month and year of first dose is not the same as the month and year of AE onset, then use the 1st of the month

- If only the month and year are specified and the month and year of first dose is the same as the month and year of AE onset, then use the date/time of first dose
- If only the month and year are specified, and the study participant did switch treatment during that month and year, then use the date of first switch treatment.
- If only the year is specified, and the year of first dose is not the same as the year of AE onset, and if the study participants did not switch from placebo to bimekizumab at Week 16, then use January 1 of the year of AE onset
- If only the year is specified, and the year of first dose is the same as the year of AE onset, then use the date/time of first dose
- If only the year is specified, and the year of first dose is the same as the year the study participant did switch treatment, then use the date of first switch treatment.
- If only the year is specified, and the year of first dose is the same as the year of the AE onset and the same as the year the study participant did switch treatment, then use the date of first dose.
- If the imputed stop date is prior to the imputed start date
 - For missing start day and start month:
 - If the year of start date is the same as the year of first dose and the imputed stop date is on or after the date of first dose then set the start date to the date of first dose
 - Otherwise set to the 1st January of the year of the start date
 - For missing start day only
 - If the month and year of the start date is the same as the month and year of first dose and the imputed stop date is on or after the date of first dose then set the start date to the date of first dose
 - If the month and year of the start date is the same as the month and year of first dose and the imputed stop date is before the date of first dose then set the start date to the 1st of that month
- If the AE onset date is completely unknown, then use the date of first dose

Imputation of Partial Stop Dates:

- If only the month and year are specified, then use the last day of the month
- If only the year is specified, then use December 31st of that year
- If the AE is resolved and the stop date is completely unknown, then do not impute the stop date

Other imputation

In addition, the following will apply for presenting AE in summary tables:

- If the intensity of an AE is unknown, it will be considered as severe.
- If the relationship to study drug is missing, it will be considered as related.

For seriousness, no imputation rule will be applied for the interim analyses, but the worst-case approach will be applied for the final analysis (ie, the missing seriousness will be considered as serious if missing).

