3.2.2.1.1 Study periods for safety data

The following study periods are defined for the classification of safety data by study period:

- Pre-treatment Period (Screening Period): Starts at the time of the informed consent date and ends prior to the day and time of the first dose administration of study drug.
- 16-Week Double-Blind Treatment Period (DBTP): Starts on the day of the first IMP administration and ends prior to the day of first IMP administration in the maintenance period (first IMP in the MP typically occurs at Week 16, but for those that miss the Week 16 IMP, first IMP in the MP will be the first IMP administration after Week 16). For study participants that withdraw from the study prior to start of IMP in the maintenance period, the DBTP ends on the day of the ET Visit.

See Section 3.7 (Treatment assignment and treatment groups) for allocation of AEs that occur on the day of IMP administration.

For vital sign parameters, the DBTP will start at the day and time of first IMP administration and ends prior to the day and the time of first IMP administration in the MP as there are 3 assessments collected at Baseline and Week 16 (one pre-dose, one 30 minutes post-dose and one 1-hour post-dose).

- 36-Week Maintenance Treatment Period (MP): Starts on the day of IMP administration at the Week 16 visit and ends 28 days (one dosing interval) after the day of last IMP administration before the Week 52 visit. For participants that do not receive IMP at the Week 16 visit, the MP starts on the day of first IMP administration after Week 16. For study participants that

withdraw from the study after Week 16 but before Week 52, the MP ends on the day of the ET Visit. In the event that no ET visit is performed, the MP ends 28 days after the last IMP administration.

For vital sign parameters, the day and the time will be used to define the MP for the same reason that given above.

- **Safety Follow-Up Period:** The SFU period will be defined for all study participants who complete the final IMP administration of the study at Week 48 and do not enter the OLE study, or for study participants who discontinue early including those withdrawn from IMP.
 - For study participants who complete the final IMP administration of the study at Week 48 and do not enter the OLE study, the SFU period starts 29 days after the day of last IMP administration before the Week 52 visit and ends on the day of the SFU Visit or on the last contact date, whichever happens later.

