3.7 Treatment assignment and treatment groups

It is expected that study participants receive treatment as randomized for the Double-Blind Treatment Period, or as assigned per protocol study design (via reallocation) for the Maintenance Period.

Hence safety analyses will be based:

- on the SS as randomized, for the Double-Blind Treatment Period (displaying data under Placebo and BKZ 160mg Q4W columns),
- on the MS as assigned treatment, for the Maintenance Period (displaying data under BKZ 160mg Q4W Total column),
- on the SS as randomized/assigned treatment for the overall period (displaying data under BKZ 160mg Q4W Total column),

However, if after unblinding it is determined that study participants randomized to placebo received bimekizumab at any time during the Double-Blind-Treatment Period, then for safety analyses these study participants will be reallocated to the bimekizumab treatment group. Study participants randomized to bimekizumab will only be reallocated to the placebo treatment group if they never received bimekizumab. For AE analyses, AEs for each study participant will be summarized based on the treatment at the onset of each particular AE. AEs that occur on the day of first IMP administration will be allocated to the treatment received on that day. For study participants randomized on placebo who switch treatment per study design at Week 16 (ie, reallocation to bimekizumab treatment), AEs will be allocated to the treatment the study participant was on the day the event occurred. If the event occurs on the day of the switch, it will be attributed to the initial treatment (ie, Placebo), unless the AE fulfills the criteria for an

anaphylactic reaction in which case it will be attributed to the new treatment (ie, bimekizumab). Specifically, this includes events meeting any of the following criteria:

- Events that fulfil the anaphylactic reaction criteria for acute events (refer to [Appendix 1](#))
- Events, that fulfil the hypersensitivity reaction criteria
- Events with an HLT of 'Administration site reactions NEC'
- Events with an HLT of 'Injection site reaction'

Efficacy analyses will be performed according to randomization and not actual treatment received. That is, if after unblinding it is determined that study participants randomized to placebo received bimekizumab at any time during the Double-Blind-Treatment Period efficacy analyses for these study participants will not be reallocated to the bimekizumab treatment group.

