4.2.3 Handling of missing data for prior and concomitant medications

Any medications with incomplete start and end dates/times will be handled according to the following rules for classification as prior and concomitant and for the calculation of relative study days. In the event of ambiguity or incomplete data which makes it impossible to determine whether a medication was concomitant or not, the medication will be considered as concomitant. Such imputations will only be performed for these classifications and calculations; in the listings all data will be shown as recorded on the electronic case report form (eCRF).

Imputation of Partial Start Dates

- If only the month and year are specified and the month and year of first dose is not the same as the month and year of the start date, and the study participant did not switch treatment during that month and year, then use the 1st of the month
- If only the month and year are specified and the month and year of first dose is the same as the month and year of the start, then use the date of first dose
 - If this is leading to a start date after the stop date of then use the 1st of the month
- If only the month and year are specified, and the study participant did switch treatment during that month and year, then use the date of first switch treatment.
- If only the year is specified, and the year of first dose is not the same as the year of the start date and the study participant did not switch treatment during that year, then use January 1 of the year of the start date
- If only the year is specified, and the year of first dose is the same as the year of the start date, then use the date of first dose
- If the start date is completely unknown, and the stop date is unknown or not prior to the date of first dose, then use the date of first dose
- If the imputed stop date is prior to the imputed start date
 - If the year of start date is the same as the year of first dose and the stop date is after the date of first dose then set the start date to the date of first dose
 - Otherwise set to the 1st January of the year of the start date

Imputation of Partial Stop Dates

- If only the month and year are specified, then use the last day of the month
- If only the year is specified, then use December 31 of that year
- If the stop date is completely unknown, do not impute the stop date

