- If the date of last dose + 28 days extends to a date beyond the date of the final visit date (not including SFU), then this calculation reverts to:

$$\text{Date of last visit (not including SFU)} - \text{Date of first dose} + 1$$

- For study participants who die, then this calculation reverts to:

$$\text{Date of death} - \text{Date of first dose} + 1$$

- For study participants who switch study treatments per study design (ie, study participants initially randomized to placebo who are re-allocated to bimekizumab treatment):

- During the DBTP (attributed to initially randomized treatment):

$$\text{Date of last dose (DBTP)} - \text{Date of first dose (DBTP)} + 28$$

Note: If date of last dose in the Initial Period + 28 days extends to a date beyond the date of first dose in the Maintenance Period, then this calculation reverts to:

$$\text{Date of first dose (MP)} - \text{Date of first dose (DBTP)} + 1$$

- During the Maintenance Period (attributed to the treatment initiated in the Maintenance Period), the study medication duration algorithm specified for the Maintenance Period in Section 10.1.2 applies.

- Definitions for time at risk during the combined treatment period will be calculated as follows:

- For study participants who do not switch study treatments per study design:

- For study participants who complete the Maintenance Period as planned and continue into an open-label study (and, therefore, do not have the SFU visit in the feeder study):

$$\text{Date of last visit} - \text{Date of first dose} + 1$$

- For study participants who die prior to the final visit:

$$\text{Date of death} - \text{Date of first dose} + 1$$

- For all other study participants, use the minimum of the following:
 - $Date of last dose - Date of first dose + 140 + 1$
 - $Date of last clinical contact - Date of first dose + 1$

This last group could include study participants who discontinue early, study participants who complete the Maintenance Period as scheduled but choose not to continue into an open-label study, or study participants who are ongoing in the SFU period at the time of the data snapshot.

- For study participants who switch study treatments per study design:

- During the DBTP (attributed to initially randomized treatment):

$$Date of first dose (MP) - 1 - Date of first dose (DPTB) + 1$$

This assumes that any study participant in this category has completed the DBTP and doses [with a new study treatment] in the Maintenance Period.

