The EAIR is defined as the number of study participants (k) with a specific AE adjusted for the exposure and will be scaled to 100 subject-years:

$$\text{EAIR} = 100 \times \frac{k}{\sum_{i=1}^n (T_{\text{Exp}(i)})}$$

where n is the total number of study participants in the respective treatment group, and $T_{\text{Exp}(i)}$ is the time of exposure for each study participant defined as:

- For study participants with the specific AE of interest: years since first dose of the study treatment to the first occurrence for the AE of interest at the level of coding evaluated (see Section 10.1)
- For study participants without the AE: the time at risk in years (see Section 10.1)

Exact Poisson 95% confidence intervals for incidence rates are calculated using the relationship between the Poisson and the Chi-square distribution (Ulm, 1990; Fay and Feuer, 1997):

$$\begin{aligned} LCL &= \frac{\chi^2_{2n,\alpha/2}}{2} \\ UCL &= \frac{\chi^2_{2(n+1),1-\alpha/2}}{2} \end{aligned}$$

where n is the number of study participants with a specific AE for the incidence rate of interest and is the basis for the number of the degrees of freedom for the chi-square quantile for the upper tail probability χ^2 .

The EAER will be the number of AEs including repeat occurrences in individual study participants divided by the total time at risk scaled to 100 subject-years and calculated using:

$$\text{EAER} = 100 \times \frac{N_{AE}}{\sum_{i=1}^n (T_{\text{Risk}(i)})}$$

where N_{AE} is the total number of AEs, n is the total number of study participants and $T_{\text{Risk}(i)}$ is the time at risk in years for each study participant.

No confidence interval will be computed for EAER.

In the following sections, all tables based on “100 subject-years” will include EAIR (with 95% confidence interval) and EAER.

As previously indicated in [Table 4–3](#), the AE summary tables described in Section [10.2.1](#) and Section [10.2.2](#) will be presented:

- on the SS for the overall period, presenting the BKZ 160 mg Total treatment column only.
- on the SS for the Double-Blind Treatment Period for the Week 24 interim analysis only, presenting the Placebo and BKZ 160mg treatment columns.
- and on the MS for the Maintenance Period for the Week 52 interim analysis only, presenting the BKZ 160 mg Total treatment column only.

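### Apart from the Section 3.7 exceptions, adverse events dated only to the month of the placebo-to-bimekizumab switch all go to placebo, and a second imputation bullet matches the same events; the effect is small.

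*SAP*

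**What the plan says.** Section 4.2.2 has two bullets that apply to an AE with a month-only start in the switch month:

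- First start-date bullet, which imputes day 1 of the onset month (quoted here without its last word): "the month and year of first dose is not the same as the month and year of AE onset, then use the 1st of the".
- Switch bullet: if "the study participant did switch treatment during that month and year, then use the date of first switch treatment".

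The corresponding first bullet for medications, in Section 4.2.3, has a further condition: "the study participant did not switch treatment during that month and year, then use the 1st of the month".

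Section 3.7 then assigns the treatment: "If the event occurs on the day of the switch, it will be attributed to the initial treatment (ie, Placebo"). Its exceptions, which go to bimekizumab, are events meeting the anaphylactic reaction or hypersensitivity criteria and events in the administration-site and injection-site high level terms. Section 10.2 repeats the rule and refers back to 3.7.

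By Section 3.2.2.1.1 the double-blind period for safety "ends prior to the day of first IMP administration in the maintenance period". That section then sends the reader to 3.7 for AEs on a dosing day.

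For participants who switch, Section 10.1.3 gives double-blind time at risk as "Date of first dose (MP) - 1 - Date of first dose (DPTB) + 1". Section 10.1.1 has no minus 1 for participants who continue into the Maintenance Period.

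**The concern.** Dating an ambiguous event to the first bimekizumab dose looks like the cautious choice, because it resembles the rule for the month of first dose. Combined with the switch-day rule it does the reverse for ordinary events. None of them can reach bimekizumab, although some must have started after the first bimekizumab dose, and the misattribution runs only in bimekizumab's favour.

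The events land in the placebo column of the double-blind AE tables, the only controlled safety comparison in the trial. Section 10.2.2 also builds its risk-difference table for the safety topics of interest on that period. One participant is 1/100 = 1.0 percentage point in a planned placebo group of 100.

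The overlap of the two bullets is a separate defect. Hypersensitivity is one of the safety topics of interest, and the arm to which a month-only hypersensitivity event belongs depends on which bullet the programmer applies.

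**Working it through.** The plan gives no figure to reproduce here, so the rules are traced and then enumerated.

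**1. Which bullets match.** The switch comes about 16 weeks (16 × 7 = 112 days) after first dose, so the switch month is never the first-dose month. A month-only AE in the switch month therefore meets the first bullet (onset month differs from first-dose month) and also the switch bullet. Section 4.2.2 states no order between them. The condition in 4.2.3 would exclude the first bullet; 4.2.2 lacks it.

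**2. Resulting arm for a placebo switcher.**

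| Event type | Switch-date bullet | 1st-of-month bullet |
|---|---|---|
| Ordinary | placebo | placebo |
| Excepted by 3.7 | bimekizumab | placebo, unless the switch is on the 1st |

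**3. How often that is wrong.** Assumption (not in the SAP): a 30-day month, with switch day and true onset day both uniform, giving 30 × 30 = 900 pairs.

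- Ordinary events, either bullet: 0% credited to bimekizumab. True onset follows the switch day in 435/900 = 48.3%, and all of these are misattributed to placebo. For a given switch day d the share is (30 − d)/30: 93% for day 2, 50% for day 15, 3% for day 29.
- Excepted events, switch-date bullet: 100% credited to bimekizumab, of which 48.3% truly began before the switch.
- Excepted events, 1st-of-month bullet: 30/900 = 3.3% credited to bimekizumab.

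**4. Number of events.** The SAP gives neither an AE rate nor a partial-date share. Illustrative assumptions: 100 placebo switchers, 200 to 400 AEs per 100 subject-years, and 2% to 10% of AEs dated to the month only.

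- AEs in the switch month: 100 × (30.4/365.25) × 2 = 16.6, up to 100 × (30.4/365.25) × 4 = 33.3.
- Month-only: 16.6 × 0.02 = 0.33, up to 33.3 × 0.10 = 3.33.
- Truly after the switch: 0.33 × 0.483 = 0.16, up to 3.33 × 0.483 = 1.61.

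**5. Events that ended before the switch.** Section 4.2.2 has a repair for an imputed stop date that precedes the imputed start. For a missing start day it covers only the month of first dose. A switch-month AE that stopped before the switch is therefore left with an imputed start after its stop.

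**6. Time at risk on the switch day.** With the switch exactly 112 days after first dose:

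- Section 10.1.1: 112 + 1 = 113 days, switch day included.
- Section 10.1.2: Maintenance time also starts on the switch day (+ 1), so the day is counted in both periods.
- Section 10.1.3: 112 − 1 + 1 = 112 days, switch day left to Maintenance and counted once.

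The difference is 1/113 = 0.9% of double-blind time at risk.

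**The case against.** The strongest reply is that this is a minor drafting matter. Both bullets give placebo for ordinary events, the switch bullet can be read as the specific rule that overrides the general one, and the expected count is around one event or fewer. Charging the imputed events to bimekizumab also creates the opposite error: on the uniform assumption, 1 − 0.483 = 51.7% of ordinary events began on or before the switch day. On time at risk, 10.1.3 already counts the day once, and including it in 10.1.1 agrees with the placebo attribution in 3.7. The point about size stands. It does not settle the excepted events, whose arm depends on an unstated order of rules, or the one-directional attribution of the ordinary ones.

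Four stronger readings are tempting, and the document does not support them.

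- *Every ambiguous event goes to placebo.* Section 3.7 sends its excepted events on the switch day to bimekizumab.
- *The events are lost.* A reader might infer this because a switch-day date falls in the Maintenance Period and the Maintenance tables are "on the MS for the Maintenance Period for the Week 52 interim analysis only, presenting the BKZ 160 mg Total treatment column only". But 3.2.2.1.1 defers to 3.7 for AEs on a dosing day, so such an event is read as belonging to the placebo double-blind column.
- *The rule breaches the SAP's own principle for ambiguous dates.* That principle says that where incomplete data "makes it impossible to determine whether the AE was treatment emergent, the AE will be considered treatment emergent". It concerns treatment emergence, which runs from the first dose of study treatment, placebo included. A switch-month event is emergent under either arm.
- *Year-only dates have the same defect.* When first dose, onset and switch share a year, 4.2.2 uses the date of first dose, so the argument does not carry over.

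**Conclusion.** The rules are wrong as written, with a small effect. For AEs outside the 3.7 exceptions, Sections 4.2.2, 3.7 and 10.2 together attribute every month-only event in the switch month to placebo, including those that began after the first bimekizumab dose. For the excepted events, two bullets of 4.2.2 give different arms and nothing says which applies.

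The number of events cannot be sized from the SAP. The 0.2 to 1.6 misattributed AEs rest wholly on the assumed AE rate, partial-date share and uniform days, and they cover AEs of all types. The 1.0 percentage point is what one moved participant would be worth for a rare safety topic; it is not an expected effect. The time-at-risk inconsistency is one day, or 0.9%. None of this threatens the safety conclusions, but the rules should be made consistent.

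**What to change.** 1. In 4.2.2, restrict the first start-date bullet to participants who did not switch in that month, using the condition already in 4.2.3.
2. State in 4.2.2, with a cross-reference in 3.7, that a month-only AE whose start is imputed to the switch date is attributed to bimekizumab and to the Maintenance Period, unless its stop date shows that it ended before the switch. Keep the placebo attribution in 3.7 for AEs with a reported switch-day onset.
3. Use one time-at-risk formula for the switch day, so that 10.1.1 and 10.1.2 do not both count it and 10.1.1 agrees with 10.1.3.

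The cost is SAP wording in 4.2.2, 3.7 and 10.1 and a small change to the AE and exposure derivations, with no new data. The downside of item 2 is that some events that began before the switch will be counted under bimekizumab. That is the conservative direction, and the stop-date condition limits it.
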